## 14. Pharmacodynamics

### 14.1. PHARMACODYNAMIC CONCENTRATION DATA

Listings of PD blood sample collection times, derived sampling time deviations, as well as levels of observed PD variables (CD19+ B cell count, IgG, and IgM) will be provided.

---

Document:

Author:

Version Number:

Version Date:

Final v1.0

10Sep2019

Template No: CS\_TP\_BS016 Revision 4

Effective Date: 01Apr2016

Reference: CS\_WI\_BS005

Change from baseline PD variables will be calculated as (observed [measured] postdose value minus baseline value). Percent change from baseline will be calculated as  $100 \times [(observed \text{ post-dose value} - baseline \text{ value}) / baseline]$ . Baseline is defined as the CD19+ B-cell count, IgG and IgM data at predose on Day 1.

The observed, change from baseline, and percent change from baseline data will be listed and summarized by treatment, study week, study day, and nominal time point, if applicable, using appropriate descriptive statistics such as n, mean, SD, CV%, minimum, median, maximum, and 95% CIs. Analyte CD19+ B cell count, IgG, and IgM data which fall below quantifiable concentrations will be set to zero for all summaries.

Plots of mean and individual observed, change from baseline, and percent change from baseline CD19+ B cell count over time by treatment will be provided following i.v. infusions.

The relationship of CD19+ B cell counts versus drug concentrations will be explored by scatter plot.

## 14.2. PHARMACODYNAMIC PARAMETERS

For PD parameter calculations, predose samples that are BLQ for observed value will be assigned a numerical value of zero for calculation of change from baseline variables. For subjects with missing (i.e., non-evaluable samples) predose samples, change and percent change from baseline will not be calculated and PD parameters will not be reported. Any other observed BLQ values will be assigned as zero and any other observed missing values will be set to missing.

The following parameters, area under the PD variable-time effect curve (AUEC), will be calculated from the change from baseline CD19+ B cell count-time data by linear trapezoidal method using actual elapsed time from dosing. The PD parameters will be derived using SAS® or Phoenix WinNonlin®.

AUEC 0-168,w1	Area under the PD variable-time effect curve (AUEC) (cells·day/μL) over the 1 st dosing interval on Week 1 from time zero (predose) to the time prior to the 2 nd dose (168 hours postdose)
AUEC 0-168,w2	AUEC (cells·day/μL) over the 2 nd dosing interval on Week 2 from time zero (predose) to the time prior to the 3 rd dose (168 hours postdose)
AUEC 0-168,w3	AUEC (cells·day/μL) over the 3 rd dosing interval on Week 3 from time zero (predose) to the time prior to the 4 th dose (168 hours postdose)

---

Document:

Author:

Version Number:

Final v1.0

Version Date:

10Sep2019

Template No: CS\_TP\_BS016 Revision 4

Reference: CS\_WI\_BS005

Effective Date: 01Apr2016

AUEC 0-168,w4	AUEC (cells·day/μL) over the 4 th dosing interval on Week 4 from time zero (predose) to 168 hours postdose
AUEC 0-w12	AUEC (cells·day/μL) from time zero (predose) on Week 1 to the time point on Week 12
AUEC 0-w28	AUEC (cells·day/μL) from time zero (predose) on Week 1 to the time point on Week 28
AUEC 0-w52	AUEC (cells·day/μL) from time zero (predose) on Week 1 to the time point on Week 52

For AUEC calculations, the actual measurement time at the end off the partial area, was used for calculation (ie, no adjustments were made for any time deviations at this scheduled sampling time point). If the change from baseline at those respective timepoints was missing, the respective PD parameters were set to missing. All AUEC parameters will also be normalized to the time interval observed by dividing by the observed interval length. Negative partial areas will be calculated into the AUEC as observed, without exclusion or modification.

The PD parameters will be summarized by treatment and study week using n, mean, standard deviation, CV%, minimum, median and maximum.

The means for CD19+ B cell AUECs will be descriptively compared between SAIT101 and MabThera® using analysis of covariance that includes a fixed effect for treatment. Least-squares means for each treatment will be presented for each treatment with corresponding 95% CIs. The difference in least-squares means (SAIT101-MabThera®) will be presented with corresponding 90% CIs.

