2.3.5 Pharmacodynamic Endpoints

The following parameters will be determined for CD19+ B-cell counts in the PK/PD sub-population of patients:

- Observed change from baseline and percent change from baseline CD19+ B-cell counts up to Week 52
- Area under the curve from time 0 to Week 1 (AUC_{0-w1}), AUC from Week 1 to Week 2 (AUC_{w1-w2}), AUC from Week 2 to Week 3 (AUC_{w2-w3}), AUC from Week 3 to Week 4 (AUC_{w3-w4}), AUC_{0-w12} , AUC_{0-w28} , and AUC_{0-w52} for the observed change from baseline and percent change from baseline CD19+ B-cell count data

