8.12 Pharmacodynamic Analyses

The PD analysis will be performed on the PK/PD sub-population. A listing of PD blood sample collection times by individual, as well as derived sampling time deviations, will be provided. A patient listing of CD19+ B cell count, IgG and IgM (observed change from baseline and percent change from baseline) by treatment, study day, and nominal time point will be presented. Change from baseline value will be calculated as (observed [measured] post-dose value minus baseline value). Baseline is defined as the CD19+ B-cell count, IgG and IgM at pre-dose on Day 1.

The observed change from baseline and percent change from baseline data will be summarized by treatment, study day, and nominal time point using appropriate descriptive statistics such as n, mean, standard deviation, %CV, minimum, median, maximum, and 95% CIs. Analyte CD19+ B cell count data which fall below quantifiable concentrations will be set to zero for all CD19+ B-cell count summaries. Plots of mean and individual observed

change from baseline and percent change from baseline over time by treatment and study day will be provided following i.v. infusions.

Where appropriate, the following PD parameters will be calculated from the observed change from baseline and percent change from baseline PD parameter-time data. Details of the parameter calculation methods will be included in the SAP:

- Observed and change from baseline up to Week 52
- Area under the PD parameters versus time curve over the 1st dosing interval (AUC_{0-w1})
- AUC over the 1st, 2nd, 3rd, and 4th dosing intervals (AUC_{0-w1} , AUC_{w1-w2} , AUC_{w2-w3} , and AUC_{w3-w4})
- AUC from time 0 to Week 12 (AUC_{0-w12})
- AUC from time 0 to Week 28 (AUC_{0-w28})
- AUC from time 0 to Week 52 (AUC_{0-w52})

The PD parameters will be summarized by treatment and study day using n, mean, standard deviation, %CV, minimum, median, maximum, and 95% CIs.

The means of PD parameters will be compared between SAIT101 and MabThera[®] using analysis of covariance that includes a covariate for baseline value. Least-squares means for each treatment will be presented for each treatment with corresponding 95% CIs. The difference in least-squares means (SAIT101/MabThera[®]) will be presented with corresponding 90% CIs.

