## 2.6. CHANGES TO ANALYSIS FROM PROTOCOL

The following updates were made:

- The PK and PD analysis sets were updated to include subjects that received at least one dose of the study drug. The PD analysis set were updated to only include subjects that have at least one measured PD variable (CD19+ B-cell count). IgM and IgG were removed from the definition of the PDS since those PD variables are measured in all subjects in the safety analysis set.
- The following criteria was not considered for the exclusion of patients from the Per Protocol Set (PPS):
  - Patient did not have available response assessment at Week 28

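### SAP 14.2 derives the CD19+ B-cell AUECs from absolute change only, without declaring the loss of the protocol's percent-change AUCs, and its model names no baseline covariate

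*SAP*

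**What the plan says.** **Protocol.** Section 2.3.5 lists AUCs for the four weekly dosing intervals and for time 0 to Weeks 12, 28 and 52, "for the observed change from baseline and percent change from baseline CD19+ B-cell count data". The synopsis repeats the list. Section 8.12 says that, where appropriate, "the following PD parameters will be calculated from the observed change from baseline and percent change from baseline PD parameter-time data", and leaves calculation details to the SAP. It compares the parameters between arms "using analysis of covariance that includes a covariate for baseline value", with a 90% CI for the difference.

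**SAP 14.2.** The seven AUECs "will be calculated from the change from baseline CD19+ B cell count-time data by linear trapezoidal method". All are in cells·day/μL; for example, the Week 12 parameter runs "from time zero (predose) on Week 1 to the time point on Week 12". The only rescaling is by time: "All AUEC parameters will also be normalized to the time interval observed by dividing by the observed interval length". The arms are compared descriptively "using analysis of covariance that includes a fixed effect for treatment", and no other model term is named.

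**SAP 14.1 and 17.6.** Observed counts, change and percent change are kept as listings, time-point summaries and plots. B-cell recovery is reported by visit and arm.

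**SAP 2.6.** The declared PK/PD changes concern analysis sets: "The PK and PD analysis sets were updated to include subjects that received at least one dose of the study drug", together with a narrower PD set definition. The only other declared change is one per-protocol criterion. Neither the percent-change AUCs nor the PD model is mentioned.

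**The concern.** Half of a listed protocol endpoint is not derived, and the section meant for such changes is silent. The scale that was kept is the one that depends on baseline. If a product removes nearly all B cells, the absolute fall is close to the whole baseline count, so the AUEC says more about where the patient started than about how deep the depletion went. The protocol handled baseline in two ways: percent-change AUCs, and a baseline covariate for the absolute ones. SAP 14.2 specifies neither.

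PD is a secondary objective, and these AUECs carry the only between-arm PD estimates with 90% CIs in SAP section 14. As specified, they could hide a real difference in depletion or show one that comes only from baseline imbalance.

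**Working it through.** The documents give no margin, power or sample size for the PD AUECs, so there is no planned figure to reproduce.

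**1. Text comparison**

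| Item | Protocol 2.3.5 / 8.12 | SAP 14.2 |
|---|---|---|
| Scale of the seven AUCs | change and percent change | change only |
| Model | ANCOVA with baseline covariate | ANCOVA, treatment the only named term |
| Listed in SAP 2.6 | – | neither difference |

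**2. Why baseline enters**

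Let B be the baseline count and f(t) the fraction of baseline remaining at time t.

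- Absolute AUEC = −B × ∫(1 − f(t)) dt
- Percent AUEC = −100 × ∫(1 − f(t)) dt

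B multiplies only the absolute version, and dividing by interval length does not remove it. SAP 17.6 defines depletion as fewer than 20 cells/μL, so a depleted patient's change lies between −B and −(B − 20). The share of baseline carried into the value is then at least (B − 20)/B. For assumed B of 100, 150, 250 and 400 cells/μL this is 80%, 87%, 92% and 95%.

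**3. How strongly the absolute AUEC follows baseline**

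Simulation of 40,000 patients per scenario, with a linear trapezoid on the protocol visit days. Assumptions, none from the documents: log-normal baseline with CV 30% to 80%, median nadir 2% or 10% of baseline, median Week 52 recovery 20% or 50% of baseline, and f independent of baseline.

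| Parameter | R² of absolute AUEC on baseline |
|---|---|
| Week 1 | 0.68–0.995 |
| Weeks 2 and 4 | 0.79–0.998 |
| 0–w12 and 0–w28 | 0.80–0.998 |
| 0–w52 | 0.65–0.98 |

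For percent-change AUECs R² is about 0, which follows from making f independent of baseline. The dependence on baseline is weakest for 0–w52, where recovery varies between patients.

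**4. Chance imbalance alone**

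Take 60 per arm (the evaluable number planned for PK), no covariate, and identical depletion in both arms. The 90% CI half-width, relative to the mean, is about 1.658 × CV × √(2/60), and √(2/60) = 0.183. For baseline CV 30%, 50% and 80% this gives 9%, 15% and 24%.

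**5. Size of the loss, and where it comes from**

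Illustrative inputs: 60 per arm, log-normal baseline with mean 1, and residual fraction 0.10 v 0.05 with SD 0.05, truncated at 0. Truncation makes the true difference about 0.046 of mean baseline, or 4.6 percentage points.

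| Analysis | Difference/SE, CV 50% | CV 80% |
|---|---|---|
| Absolute change, treatment only | 0.55 | 0.36 |
| Absolute change, baseline covariate | 4.8 | 4.2 |
| Percent change | 5.5 | 5.5 |

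The percent-change entry is 4.6/0.84 = 5.5. The covariate recovers (4.8 − 0.55)/(5.5 − 0.55) = 86% of the gap at CV 50% and (4.2 − 0.36)/(5.5 − 0.36) = 75% at CV 80%.

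**The case against.** Five points can be made in the SAP's favour.

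- **The covariate does most of the damage.** A reader might attribute the whole drop from 5.5 to about 0.5 to the missing percent scale. Step 5 shows otherwise: with the protocol's own covariate, absolute change reaches 4.2 to 4.8. This stands. The SAP still calls its model an analysis of covariance, so a baseline term may have been intended, but none is named.
- **Depth of depletion remains visible.** A reader might infer that the SAP has removed the only measure able to show a difference in depletion. The documents do not support that. SAP 14.1 keeps observed counts and percent change by time point, with 95% CIs and plots, and 17.6 keeps B-cell recovery. What is lost is the time-integrated percent summary and its between-arm interval.
- **No formal conclusion is at risk.** A reader might infer that a PD similarity claim could be reached wrongly. There is no PD margin or similarity criterion, and the comparison is descriptive. This stands.
- **The protocol leaves latitude.** Section 8.12 is qualified by appropriateness and defers details to the SAP. That covers how a parameter is computed. It does not quietly remove one that 2.3.5 lists without qualification.
- **The simulations favour percent change.** They take the residual fraction as independent of baseline, and step 5 also holds it constant over time. Percent change can be unstable at low baseline counts. This stands as a limit on the figures, not on the text comparison.

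**Conclusion.** The inconsistency is established from the text alone: the percent-change AUCs are protocol endpoints, SAP 14.2 does not derive them, and SAP 2.6 does not say so. The protocol's baseline covariate is likewise unnamed in the SAP model and undeclared.

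That absolute-change AUECs mainly track baseline is an inference. It holds when depletion is near complete and is weaker for AUEC0–w52. The documents give no baseline counts or variability. With the stated illustrative inputs, the planned estimate reaches about 0.4 to 0.55 standard errors, against 4.2 to 4.8 with the covariate and 5.5 on the percent scale. Roughly three quarters or more of that loss is due to the covariate.

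The consequence is confined to a descriptive secondary analysis. The ORR equivalence test and the PK similarity rule are untouched. The point should be corrected, but it does not threaten the trial's main conclusions.

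**What to change.** 1. In SAP 14.2, also derive each of the seven AUECs from percent-change data, and report the between-arm difference with its 90% CI. Set the value to missing when the baseline count is zero. This rule is needed because a predose value below quantification is set to zero and would otherwise be the divisor.
2. In the absolute-change ANCOVA, name baseline CD19+ count as the covariate, as protocol 8.12 states.
3. If either departure is intended, list and justify it in SAP 2.6.

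The cost is SAP wording, one more model term, and a second run of the same trapezoidal derivation on data already collected. No new samples or visits are needed.

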## 15. Exploratory Analysis of ADA on PK and PD

An exploratory statistical assessment of the impact of overall ADA status (positive or negative) on PK across treatments will be completed by adding this covariate to the model used in the primary statistical analysis.

Overall ADA status will be defined as ADA positive if a positive ADA result occurred at any timepoint up to Week 28 (for Week 28 analysis for PK and PD and for final analysis for PK only) or up to Week 52 (for PD, final analysis). Subjects without a positive ADA result at any timepoint are considered ADA negative.

The ratio of geometric means for ADA positive/ADA negative will be reported with the 90%

---

Document:

Author:

Version Number:

Version Date:

Final v1.0

10Sep2019

Template No: CS\_TP\_BS016 Revision 4

Effective Date: 01Apr2016

Reference: CS\_WI\_BS005

CI for this ratio. Descriptive statistics for rituximab concentrations and the primary PK parameters will also be presented by ADA status. Mean PK profiles will be plotted by treatment and ADA status on linear and semi-log concentration scales.

The impact of ADA on PD (observed CD19+ B cell counts) will be explored graphically. Mean PD profiles will be plotted by treatment and overall ADA status on a linear scale.

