#### **4.4. SAFETY ANALYSIS SET [SAF]**

The Safety Analysis Set (SAF) consists of all RAN patients who received at least one dose of study drug. Patients will be analyzed according to the treatment received. SAF is used as the basis for all safety analyses.

If there is any doubt whether a patient was treated or not, they will be assumed treated for the purposes of analysis.

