#### 4.6. PHARMACOKINETIC ANALYSIS SET [PKS]

The PKS will include all patients who receive at least one dose of study drug, have at least one measured drug serum concentration at a scheduled time point post-dose, and have no major protocol deviations or violations thought to significantly affect the PK of the drug (see section **Error! Reference source not found.**).

Patients in the PKS will be analyzed according to the treatment received.

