### 6.2. MISSING DATA

Partial date will be imputed for the identification of treatment-emergent adverse events (TEAEs), prior/concomitant medication, calculation of demographic information and

---

Document:

Author:

Version Number:

Version Date:

Final v1.0

10Sep2019

Template No: CS\_TP\_BS016 Revision 4

Effective Date: 01Apr2016

Reference: CS\_WI\_BS005

medical history. Rules will be discussed in Appendix 1 of this SAP.

Main efficacy data will be handled in Section 15.1.2 and 15.2.2 of this SAP.

Missing PK concentrations will be handled as described in Section 13.

Unless otherwise specified, missing data will not be imputed in this study.

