## **16.3. EXPLORATORY EFFICACY**

### **Subgroups**

The primary efficacy endpoint will be repeated for each of the following subgroup categories as exploratory efficacy analyses based on the FAS and the PPS.

- Region – EU, Others (including US)
- Age group – 18-60 years, >60 years
- Gender – Female, Male
- ADA status – Positive at any time up to Week 28, Negative at all time points

The same statistical method (as defined in Section 16.1.3) will be used for each subgroup category. The adjusted proportion difference in ORR and corresponding 95% CI according to the primary analysis will also be presented in a Forest plot. The interaction p-value for the subgroups being examined will be calculated based upon the full set of data (not subset for each subgroup category being examined), and will be based on primary CMH

---

Document:

Author:

Version Number:

Version Date:

Final v1.0

10Sep2019

Template No: CS\_TP\_BS016 Revision 4

Effective Date: 01Apr2016

Reference: CS\_WI\_BS005

model to which the variable for the subgroup being examined will be added as an additional stratification factor. The p-value will be calculated using Gail-Simon Test for Qualitative Interactions, specifying that we are interested in the subgroup variable risk differences.

As mentioned in section 3.3, additional exploratory subgroup analyses may be performed as ad hoc analyses if deemed necessary. The subgroups to be used for this analysis may be based on, but not limited to, the results of analysis of PK, PD, efficacy, safety, immunogenicity and concomitant medication.

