### 18.1. ADA

The incidence of ADA and neutralizing antibody at Day 1 pre-dose and at Weeks 2 pre-dose, 3 pre-dose, 4 pre-dose, Week 5, 12, 20, 28, 36, and 52 (EOS) will be summarized by treatment group and visit.

- Incidence (%)= number of subjects with specific assessment result/ number of subject with available assessment results \* 100%

ADA and neutralizing antibody results by visit as well as the overall positive of ADA and neutralizing antibody from Day 1 will be summarized. Patients with at least one positive result up to Week 28 (or Week 52) from (and including) Day 1 will be considered as overall positive; Otherwise, patients without any positive result up to Week 24 (or Week 52) from (and including) Day 1 will be considered as overall negative.

For each treatment group, the proportion of response, 95% CI for the proportion, proportion difference between SAIT101 and MabThera®, standard deviation, and 95% CI for the proportion difference will be reported. The Wilson Score method will be used to calculate 95% CI.

- Response:
  - ADA positive
  - ADA negative
  - Neutralizing antibody positive
  - Neutralizing antibody negative

Listings for ADA assessments by patient will be provided.

---

Document:

Author:

Version Number:

Version Date:

Final v1.0

10Sep2019

Template No: CS\_TP\_BS016 Revision 4

Effective Date: 01Apr2016

Reference: CS\_WI\_BS005

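### Overall ADA status defaults to negative, so a treated patient with only a pre-dose sample (or, under SAP 15, no ADA result at all) is classed as ADA negative

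*SAP*

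**What the plan says.** **Overall status.** SAP 15: "Overall ADA status will be defined as ADA positive if a positive ADA result occurred at any timepoint up to Week 28" (Week 52 for PD in the final analysis). Everyone else falls under one sentence: "Subjects without a positive ADA result at any timepoint are considered ADA negative". SAP 18.1 sets the same default for the immunogenicity tables: "patients without any positive result up to Week 24 (or Week 52) from (and including) Day 1 will be considered as overall negative". The matching clause for overall positive runs to Week 28 (or Week 52). The Day 1 sample is taken before dosing (Protocol Table 1, footnote w).

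**Incidence.** SAP 18.1 computes it as "number of subjects with specific assessment result/ number of subject with available assessment results".

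**Response subgroup.** SAP 16.3 words the split as "ADA status – Positive at any time up to Week 28, Negative at all time points" and does not mention missing time points.

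**Entry to the analysis sets.** The Safety Analysis Set takes "all RAN patients who received at least one dose of study drug". The PK set needs one dose, no relevant major deviation, and that patients "have at least one measured drug serum concentration at a scheduled time point post-dose". Neither asks for an ADA result.

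**Missing data in general.** SAP 6.2: "Unless otherwise specified, missing data will not be imputed in this study".

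**Where the status is used.** It defines PK parameter summaries and is a covariate in the PK sensitivity model (13.2). It is the factor in the exploratory analysis (15). Section 18.1 reports ADA proportions and the difference between arms with a 95% CI.

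**The concern.** A negative overall status should mean that the patient was tested after exposure and no antibodies were found. As written, it means only that no positive result is on file. A sample drawn before the first infusion says nothing about antibodies induced by study drug, and an absent sample says nothing at all.

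Immunogenicity is a secondary objective of a biosimilarity trial. The overall ADA proportion per arm, with the difference between arms, is a natural headline for it. Untested patients counted as negative dilute that proportion. If they are unevenly spread between arms, they also shift the difference. The same label is used to compare PK between ADA-positive and ADA-negative patients, where untested patients blur the negative group.

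**Working it through.** **1. Who is classed how.** All rows are treated patients with no positive result.

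| Evaluable ADA results | SAP 15 | SAP 18.1, overall | SAP 18.1, by visit |
|---|---|---|---|
| None | Negative | Negative by the wording, but probably outside the denominator | Not counted |
| Day 1 pre-dose only | Negative | Negative, and inside the denominator because a Day 1 result is an available result | Counted at Day 1 only |
| At least one post-dose | Negative | Negative | Counted at visits sampled |

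Only the last row supports the label. The SAP does not say whether the 18.1 formula also governs overall status, hence the qualified entry in the first row.

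**2. Whether another rule closes the gap.** The two analysis sets do not, because entry needs a dose or a drug concentration. The no-imputation rule in 6.2 does not, because it gives way to anything specified otherwise and Section 15 does specify. The subgroup wording in 16.3 is stricter in tone but silent on missing samples.

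**3. The route into PK.** Under SAP 13.2, Cmax,w1 needs only the end-of-infusion concentration. A patient who leaves the study after the first infusion can contribute Cmax,w1 while classed negative on a pre-dose sample alone. AUC over the first interval needs the Week 2 pre-dose concentration, and AUC over the fourth needs Week 5. Protocol Table 1 and SAP 18.1 schedule ADA at both visits, so AUC is largely protected. One inconsistency weakens this: Protocol Appendix 10, Section 2.2, limits treatment-visit immunogenicity sampling to Day 15. If that were followed, a patient leaving between Day 8 and Day 15 could have a first-interval AUC but no post-dose ADA result.

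**4. Scale.** The documents give no ADA rate, no ADA sample-loss rate and no ADA margin, so there is no figure to reproduce. The following is illustration under assumptions only.

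- *Overall proportion.* Let p be the positive proportion among patients with an evaluable post-dose result, and m the share of the denominator without one, all called negative. Reported proportion = p(1 − m); under the fix it is p.

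| Assumed p | m = 2% | m = 4% | m = 10.4% |
|---|---|---|---|
| 2% | 1.96% | 1.92% | 1.79% |
| 10% | 9.8% | 9.6% | 9.0% |
| 20% | 19.6% | 19.2% | 17.9% |

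The 4% borrows the protocol's allowance for drop-out and major deviations (Section 8.4). The 10.4% borrows the PK over-recruitment, (134 − 120)/134. Neither is a rate of loss before the first post-dose ADA sample. One affected patient in an arm of 154 gives 10% × 153/154 = 9.94%.

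- *Arm difference.* With equal p, the spurious difference is p(m₁ − m₂). Assumed losses of 10% and 2% give 10% × 8% = 0.8 points at p = 10% and 20% × 8% = 1.6 points at p = 20%. The approximate 95% half-width with 154 per arm is 1.96 × √(2 × 0.10 × 0.90/154) = 6.7 points at p = 10% and 8.9 points at p = 20%. In an arm of 154, 0.8 points is 1.2 patients.

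- *PK ratio, ADA positive to negative.* The share of the negative group that is truly positive is c = mq/[m + (1 − m)(1 − p)], with q the ADA rate among untested patients. The apparent ratio is exp[(1 − c) ln R], with R an assumed true ratio of 0.70. For p = 10% and m = 4%, the denominator is 0.04 + 0.96 × 0.90 = 0.904. Then q = 10%, 50% and 100% give c = 0.4%, 2.2% and 4.4%, and apparent ratios of 0.701, 0.706 and 0.711. At the extreme (p = 20%, m = 10.4%, q = 100%), c = 12.7% and the ratio reads 0.733.

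**5. Direction.** The reported proportion cannot exceed p, but whether it understates drug-induced ADA is open. Both sections let a Day 1 pre-dose positive count as overall positive, which pushes the other way, and q is unknown.

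**The case against.** A reader might infer that missing ADA data in general are scored as absence of antibodies, that overall incidence is therefore understated, and that a material false difference between arms follows. The documents do not support that.

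- **Few patients can qualify.** ADA is scheduled at ten visits and at the early treatment discontinuation visit. Patients who stop study drug are followed to Week 52 for immunogenicity (Protocol 3.3.1.2). To have no post-dose result, a dosed patient must in practice leave almost at once.
- **By-visit incidence is sound.** It uses patients with a result. If the same denominator governs overall status, 18.1 is left with Day-1-only patients.
- **No decision turns on it.** The PK similarity model has no covariates. ADA status enters summaries, a sensitivity model, a response subgroup and an exploratory analysis. No ADA margin is set.
- **The loss rates are hypothetical.** Even 10% against 2% gives differences far inside the sampling error shown above.
- **The fix is partial.** A patient with one early post-dose negative and nothing later remains negative.

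All of this stands as a limit on reach and size. None of it alters the fact that the stated rule gives the wrong label to the patients it touches. The rule is explicit, so this is more than an unstated detail.

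**Conclusion.** The point holds as a minor defect of definition. SAP 15 and 18.1 make negative the default for overall ADA status without requiring any post-dose result. The affected results are the overall ADA proportion and arm difference in 18.1, the PK summaries and sensitivity model (mainly through Cmax,w1), and the Section 15 analysis. By-visit incidence, the PK similarity conclusion and the primary efficacy analysis are untouched.

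The number of patients is probably small. Size and direction cannot be stated from the documents; every rate in the illustration is an assumption. In 18.1 the reach also depends on whether the available-results denominator applies to overall status, which the SAP leaves open.

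**What to change.** In SAP 15 and 18.1, define overall negative as no positive result and at least one evaluable post-dose ADA result in the period. Class the remaining patients without a positive result as not evaluable, exclude them from the overall denominator, and report their number per arm. State that the available-results denominator governs overall status.

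In the same sentence of 18.1, reconcile Week 28 for positive with Week 24 for negative: Protocol Table 1 has no Week 24 visit. As written, a patient first positive at Week 28 meets the positive clause and also has no positive result up to Week 24. Protocol Appendix 10 and Table 1 also need reconciling on ADA sampling at the treatment visits.

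The cost is about a sentence in each SAP section and a slightly smaller denominator. No new data are needed.
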